4 STUDY DESIGN

4.1 OVERALL DESIGN

This is a controlled, single-blind, cross-over study design that will enroll 10 subjects suffering from moderate to severe AD with an MMSE of 5-20 and no neuropsychiatric symptoms of dementia. The study is designed to compare the effects of musical intervention consisting of an emotionally impactful tune unique to the subject versus a control intervention consisting of nature sounds.

The study will involve five visits one week apart from each other. The first visit will be a Screening Visit in which informed consent will be obtained, eligibility will be evaluated, an auditory assessment will be administered, and demographics and medical history will be recorded. If eligibility is confirmed, the subject will progress to the Baseline Visit. At the Baseline Visit, the CGIC, SSS, and SIB-8 will be administered, and an interview will be conducted. During the interview, three musical tunes that have a positive meaning to the subject will be identified. After the Baseline Visit and before Visit 1, one tune will be randomly selected out of the three to be used as the experimental intervention.

A randomization program will be used to deliver either the selected musical tune or nature sounds via over-ear headphones at Visit 1. Visit 2, which will occur a week later, will be identical to Visit 1, but the subjects that were originally exposed to music will hear nature sounds and vice versa. Over the course of a 3-hour session during Visit 1 and Visit 2, both interventions will be delivered as 10-minute segments at the top of each hour. After each musical intervention, the subjects will remain in the same research environment and will be free to interact with their caregivers and the staff until the next round of music is performed. The third and final interventional segment will be followed by the administration of the CGIC, SSS, and SIB-8. Finally, at Visit 3, subjects will complete three consecutive 10-minute fMRI scans: resting state (baseline measure), preferred music, and nature sounds, to be administered in a randomized order. The resting state fMRI will serve as the baseline reading. All measures will be done between 9am and 1pm.

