Auditory acuity will be evaluated to determine the intensity of the sound the subjects are exposed to. Specifically, the level of sound the subjects are exposed to will be calibrated in relation to their hearing abilities in order to assure a similar level of music stimulation in all subjects. We will use a well-established hearing test, pure-tone audiometry, to perform this evaluation on the study population²⁴.

The goal of the fMRI scans is to determine whether the preferred music intervention enhances connectivity with brain networks associated with arousal as compared to pure resting state and nature sounds. The primary outcome measure for connectivity will be a measure of entropy or spread of information from the auditory cortex to other parts of the brain.

Our chosen MMSE score for the study is 5-20 points. The MMSE is a test designed to evaluate basic cognitive functions and is often utilized to gauge the level of impairment in patients with AD. The MMSE is scored is 0-30, with scores of 20 to 24 suggesting mild dementia, scores of 13 to 20 suggesting moderate dementia, and scores of less than 12 suggesting severe dementia.

On average, the MMSE score of a person with AD declines about two to four points each year. As stated, a MMSE score of 20 usually reflects a patient in the moderate stages of the disease where brain degeneration starts to become more pronounced, but where we believe auditory areas remain almost intact. The lower score of 5 reflects the severe stages of the disease where we believe even auditory areas of the brain engaged in music activation will start to be affected, thus scores below 5 will be excluded.

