MRI scanning includes collection of a high-resolution T1-weighted MPRAGE (TR=2.3s, TE=2.23ms, flip angle=8°, 192 sagittal slices, FOV=256x256mm), followed by a 10-minute resting state fMRI scan and two 10-minute stimulation scans (nature sounds/preferred music; acquisition parameters: 3 mm³ voxels, TR=1.1s, TE=30 ms, flip angle=65°, 51 axial slices, matrix=64x64, 375 time points, acceleration factor=3). Gradient field maps will also be collected. More information about fMRI resources will be provided upon request.

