9 STATISTICAL CONSIDERATIONS

Initially, baseline variables and outcomes (Clinical Global Impression of Change, Stanford Sleepiness Scale) will be summarized using descriptive statistics for each intervention. For the primary comparison of outcomes between visits 1 and 2, general linear mixed models will be constructed. GLMMs are an excellent means of accounting for clustering (correlation) of observations within subjects over time, which naturally occur as a part of crossover designs such as this. The models for CGIC, SSS and SIB-8 will include main effects for sequence (intervention order), period (a subject's first or second trial), and intervention (music vs. nature sounds), along with random subject effects. Since this is a pilot study of n=10, the focus will be on estimating group differences as opposed to formal hypothesis testing. The estimates provided by the GLMMs will be vital for designing a future more definitive crossover trial.

For fMRI analysis based on data from Visit 3, we will use analytic methods similar to those used in our prior publications of functional network connectivity²⁵⁻²⁹ and similar to other studies³⁰. Briefly, following fMRI preprocessing and nuisance signal regression, residual time series from each of 294 brain regions (nodes) will be submitted to partial correlation to establish the connectivity between each pair of nodes in the network, controlling for connectivity of all other nodes. These pair-wise correlations then serve as edge weights in the calculation of graph-theory measures like diversity coefficient.

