The Brain Connectivity Toolbox (BCT)³¹ will be used to calculate diversity coefficient after establishing the community structure in each participant using modularity and consensus functions. Modularity will be run 1000 times for each subject, and the consensus community structure, as implemented in the BCT, will be determined. The diversity coefficient of the auditory cortex will be the primary measure of interest. The higher the diversity coefficient of the auditory cortex, the greater the spread of information to other networks in the brain [JL2] [a3]. Visualization of the connectivity of the auditory cortex as measures by diversity coefficient is expected to reveal greater connectivity with frontal and fronto-parietal networks associated with arousal in the preferred music condition compared to continuous resting state or nature sound conditions. A separate GLMM will then be used to determine whether the diversity coefficient differs by intervention; this model will include main effects for

sequence (intervention order) and intervention (because there is only one MRI session, period is not applicable), along with random subject effects.

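### The fMRI model drops period although Visit 3 has three ordered scans per subject, and the documents leave the scan order unclear

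*Combined protocol and SAP*

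**What the plan says.** Section 9 (Statistical Considerations) fits the diversity coefficient of the auditory cortex with sequence, intervention and random subject effects. Period is left out "because there is only one MRI session, period is not applicable". For the clinical outcomes the same section keeps it: "The models for CGIC, SSS and SIB-8 will include main effects for sequence (intervention order), period", where period is a subject's first or second trial.

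Section 4.1 (Overall Design) describes Visit 3 as "three consecutive 10-minute fMRI scans: resting state (baseline measure), preferred music, and nature sounds, to be administered in a randomized order", and adds that the resting scan serves as the baseline reading. Section 8.2 (Functional Network Analysis) describes the acquisition as a structural scan "followed by a 10-minute resting state fMRI scan and two 10-minute stimulation scans", without mentioning randomisation.

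Section 4.2 gives the imaging goal as finding out whether preferred music "enhances connectivity with brain networks associated with arousal as compared to pure resting state and nature sounds". The fMRI evaluation is listed under both the primary and the secondary endpoints. Section 9 also says: "The estimates provided by the GLMMs will be vital for designing a future more definitive crossover trial".

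**The concern.** In a crossover, period is the ordinal position of a measurement within a subject. It does not depend on how many visits there are. Three back-to-back scans have three positions, and fatigue, habituation, drowsiness or head motion could plausibly change across them. Section 9 adjusts for this kind of effect in the clinical models and sets it aside in the imaging model for a reason that the Visit 3 design contradicts.

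The consequence depends on the scan order, which the documents do not settle:

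- **All three scans randomised.** An omitted drift adds chance imbalance to the music–nature estimate and inflates the residual variance. Both matter in a pilot of 10 whose stated focus is estimation and whose estimates are meant to inform the next trial.
- **Rest always first.** Every comparison with rest is mixed with position. That is half of the imaging goal in Section 4.2.

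**Working it through.** **Inputs.** From the documents: n = 10, three scans per subject, three conditions. There is no stated figure to reproduce, since the plan gives no effect size, SD or precision for this outcome. Assumed: a linear drift of d residual SDs per scan position, with d = 0, 0.25, 0.5 or 1. Residual SD is set to 1. Models have subject and condition effects, with or without a scan-position factor.

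**The sequence term.** Sequence is constant within a subject, so it drops out of any within-subject contrast. As a check, I put rest first and split the music/nature order unevenly. With position omitted, the music–nature bias is d × (difference in order counts)/10: 0.20d at 6/4 and 0.40d at 7/3. Adding sequence left these figures unchanged; adding position made them zero. Under simple randomisation an exact 5/5 split has probability 0.246, and 7/3 or worse about 0.34.

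**All three scans randomised.** Over the six orders, music and nature differ by one position in four and by two positions in two. The mean squared difference is (4×1 + 2×4)/6 = 2.

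- Simple randomisation: the imbalance in mean position has SD √(2/10) = 0.45. The SD of the estimate without the term is √(0.2 + 0.2d²), which is 0.45, 0.46, 0.50 and 0.63. Residual variance is inflated by 1 + d², that is by 6%, 25% and 100% for d = 0.25, 0.5 and 1.
- Near-even allocation (four orders twice, two once, chosen at random): the imbalance SD is √3.2/10 = 0.18, and residual variance is inflated by about 1 + 1.09d².

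Simulation (6,000 replicates per cell) for music–nature:

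| | d=0 | 0.25 | 0.5 | 1 |
|---|---|---|---|---|
| Simple: SD without term | 0.446 | 0.465 | 0.507 | 0.633 |
| Simple: SD with term | 0.474 | 0.479 | 0.483 | 0.475 |
| Simple: 95% half-width without | 0.929 | 0.950 | 1.039 | 1.314 |
| Simple: 95% half-width with | 0.996 | 0.988 | 0.995 | 0.994 |
| Near-even: SD without term | 0.445 | 0.449 | 0.461 | 0.479 |
| Near-even: SD with term | 0.449 | 0.451 | 0.454 | 0.448 |
| Near-even: 95% half-width without | 0.926 | 0.963 | 1.048 | 1.344 |
| Near-even: 95% half-width with | 0.940 | 0.946 | 0.946 | 0.940 |
| Near-even: coverage without | 95.1% | 95.5% | 96.8% | 99.2% |

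Break-even on half-width:

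- Simple: 0.929√(1+d²) = 0.993 gives d ≈ 0.38.
- Near-even: 0.926√(1+1.09d²) = 0.942 gives d ≈ 0.18.

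**Rest always first, music/nature 5/5.** Rest is at position 1 and the other two average position 2.5, so music–rest and nature–rest are each biased by 1.5d: 0.375, 0.75 and 1.5. A position factor does not help. The three-condition design matrix then has rank 13 with 14 columns, so stimulation versus rest is aliased with position.

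Music–nature is unbiased, but without the term its SE is inflated by √(1 + (10/9)d²/2) = 1.02, 1.07 and 1.25 for d = 0.25, 0.5 and 1. The half-width is 0.98, 1.00, 1.05 and 1.23 at d = 0, 0.25, 0.5 and 1, against 1.00 throughout with a two-level position term.

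**The case against.** The strongest defence is that Section 9 uses period for the comparison of Visits 1 and 2, and in that visit-level sense one MRI session has no period. Section 4.1, the design section, states randomisation, while Section 8.2 is a paragraph of acquisition settings that never says the order is fixed. Under full randomisation inference stays valid. Coverage without the term under simple randomisation, re-run with 1,500 replicates, was 94.5%, 96.0%, 94.1% and 95.5% across the four drifts. The term costs precision when drift is small, and an overstated variance makes a later sample size too large rather than too small.

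Much of this stands. The loss under full randomisation is one of precision, its size is unknown, and under simple randomisation the term is a net loss at d = 0 and 0.25. It does not rescue the stated reason, because a visit-level reading still leaves three ordered measurements per subject unadjusted. Nor does it settle the order, because calling rest the baseline and listing it first both point to a fixed first scan.

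Two further ambiguities are fair to raise. Intervention in this model could have two levels (music, nature) or three. With complete data, music–nature without a position term is the mean within-subject difference either way, so its SD above is unchanged; only the degrees of freedom and interval width differ. Sequence could mean the Visit 1/2 order or the Visit 3 scan order. If it means six scan orders, it takes five between-subject degrees of freedom but does not touch the within-subject contrasts.

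**Conclusion.** The point holds and should be fixed before Visit 3 scanning starts. That period applies, and that sequence cannot replace it, follows from the design and needs no assumption about drift. The practical size does depend on drift, which the documents do not give.

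With all three scans randomised, omitting position leaves music–nature valid on average. It costs little below about 0.2 to 0.4 residual SD of drift per position. At 1 residual SD, the interval is roughly 30% to 40% wider than with the term (1.314 against 0.994 under simple randomisation, 1.344 against 0.940 under near-even allocation), and the residual variance available for planning is about doubled.

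The more serious consequence follows if rest is always first. Contrasts with rest are then confounded with position by 1.5 times the drift, whatever model is fitted. All figures assume linear drift, independent residuals, complete data and no carryover.

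**What to change.** 1. Reconcile Sections 4.1 and 8.2 on whether all three scans or only the two stimulation scans are randomised. This has to be settled before scanning.
2. In Section 9, delete the statement that period does not apply. Specify fixed effects for Visit 3 scan order, scan position (first, second, third) and condition, with a random effect for subject. State whether condition has two or three levels.
3. If all three scans are randomised, use four of the six orders twice and two once. Making the two single-use orders mirror images of each other gives every condition the same mean position, which removes linear-drift bias from all contrasts; the position term is then needed only to remove the residual inflation.
4. If rest is first, balance the music/nature order 5/5 and base the model on music versus nature with a two-level position term. Report contrasts with rest as descriptive and confounded with position.
5. Note carryover between scans as a limitation, or examine it in an optional sensitivity analysis. Section 4.3 expects music effects to fade over about three hours, and a position term does not address this.

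The cost is revised wording, an allocation list and two model degrees of freedom (one if rest is first). If there is no drift, the 95% interval is about 7% wider under simple randomisation (0.996/0.929), 1.5% with near-even allocation (0.940/0.926) and 2% in the rest-first 5/5 case (1.000/0.984).

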10 SUPPORTING DOCUMENTATION AND OPERATIONAL CONSIDERATIONS

10.1 REGULATORY, ETHICAL, AND STUDY OVERSIGHT CONSIDERATIONS

10.1.1 INFORMED CONSENT PROCESS

If the subject meets these basic criteria, the PI will present an Informed Consent Form (ICF) to both the subject (and if applicable the subject's legal authorized representative) and the caregiver/informant to participate in the study. After the Informed Consent is fully discussed, and all questions are answered, another designated investigator determines whether the subject has the capacity to provide their own informed consent. For those subjects with Decision Capacity, the subject will then sign their own ICF. For those subjects without Decision Capacity, the subject's legal authorized representative by SC state law will be asked by the investigator obtaining consent to sign the ICF, with verbal assent from the subject.

The PI will also present the HIPAA Authorization form, which will be fully discussed with the subject. All questions will be answered by the PI and the specifics of the Notice of Privacy Practices will be explained. The subject and the subject's legal authorized representative (if applicable) will sign the HIPAA Authorization form thereafter. A copy of the signed ICF, the signed HIPAA Authorization form, and the Notice of Privacy Practices will be given to the subject.

Decision Capacity

Decision capacity is determined every time an informed consent is executed, regardless of subject's clinical presentation. Subjects are evaluated by a clinician (MD or master level clinician) independent of the study team to determine if they have decision capacity. If the subject does not have decision capacity, a legally authorized representative (spouse, all next of kin, or individual with healthcare power of attorney) will be required to review and sign the Informed Consent.

The decision capacity determination will be completed on a separate form which states the study subject's ability to make a decision regarding participation in the study and then dated and signed by the clinician who made the determination.

Decision capacity process will be repeated for any new informed consents using the same procedures as above.

Research subjects are free to withdraw informed consent at any time if they desire to do so. Appropriateness of a research subject's involvement in a research study is evaluated on an ongoing basis by the PI.

It should be noted that the ability to provide informed consent is based on decision capacity at the time of administration of the informed consent, not on the severity of the disease. If the subject has agreed to participate in the study and the study procedures, the subject will not need to be reassessed for decision capacity given the short duration of the study.

10.1.2 CONFIDENTIALITY AND PRIVACY

Participant confidentiality and privacy is strictly held in trust by the PI and his staff and their interventions. The study protocol, documentation, data, and all other information generated will be held in strict confidence. No information concerning the study or the data will be released to any unauthorized third party without prior written approval of the subject.

All research activities will be conducted in as private a setting as possible.

Representatives of the IRB or regulatory agencies may inspect all documents and records required to be maintained by the PI. The clinical study site will permit access to such records.

The study participant's contact information will be securely stored at the clinical site for internal use during the study. At the end of the study, all records will continue to be kept in a secure location for as long a period as dictated by the reviewing IRB or Institutional policies.

Study participant research data, which is for purposes of statistical analysis and scientific reporting, will be transmitted to and stored at the Medical University of South Carolina. This will not include the participant's contact or identifying information. Rather, individual participants and their research data will be identified by a unique study identification number. The study data entry and study management systems used by the clinical site and by the Medical University of South Carolina research staff will be secured and password protected. At the end of the study, all study databases will be de-identified and archived at the Medical University of South Carolina.

10.1.4 PROVISIONS TO MONITOR THE DATA TO ENSURE THE SAFETY OF SUBJECTS

Data safety and monitoring will be carried out to ensure and maintain the safety of our participants. Safety monitoring is the process during the study that involves the review of accumulated outcome data to determine if any of the procedures practiced should be altered or stopped. Due to scope and limited risk of the protocol as well as lack of significant risk of listening to music intervention, no Data Safety Monitoring Board is required. However, the study Safety Monitor will be responsible for monitoring the safety of the study and complying with the reporting requirements. Continuous, close monitoring of participant safety will include prompt reporting of safety data (i.e., adverse/serious adverse events) to the MUSC IRB. Serious adverse events will be reported to IRB within 48 hours of the time project staff become aware of the incident. Safety Monitor will review study data and procedures if early termination of the study, amendment to the protocol, or changes to the data collection plan are needed. Should the protocol or data collection plans be amended as a result of data review, the IRB will be notified and the amendment approved prior to study amendment implementation. In addition, the participants will be notified of any significant new findings that develop during the course of research (e.g., other potential risks) that may affect their wish to continue participation in the study.

10.1.5 QUALITY ASSURANCE AND QUALITY CONTROL

The data system will employ double data entry and range checks to reduce the occurrence of data entry errors. The Data Management Team will also develop and periodically run data quality query programs on all the accumulated data to check the logic and consistency of data between forms and provide additional means of detecting errors. Queries generated during this process will be sent to the clinical center where personnel will attempt to resolve the queries. Any changes to the data will be made on the CRFs and in the data system. All changes made to the data system will be logged and information including data systems operator making the change, details of change, date, and time will be recorded.

10.1.6 DATA HANDLING AND RECORD KEEPING

DATA COLLECTION AND MANAGEMENT RESPONSIBILITIES

Prior to completing any protocol procedures:

- 1. The PI and the coordinator have complete the Collaborative Institutional Training Initiative (CITI) course on protections of human subjects in research. The CITI was founded in March 2000 as collaboration between the University of Miami and the Fred Hutchinson Cancer Research Center to develop a web-based training program in human research subjects' protections.
- 2. The PI has successfully completed training for administering the MMSE, TUG, MRI Metal Screening Questionnaire, CGIC, SSS, and SIB-8.

The PI is trained to perform vital signs.

This is a single site study, and individual data will not be shared with any other research site. The data collected will not contain any identifiers. No identifying data is shared with any source outside the local research team without specific release of information from the subject.

Data will be stored in a locked office within a locked suite only accessible to authorized personnel. The research data will be stored and managed in REDCap, a secure web-based database system designed for clinical research studies.

Types of Raw Data

Raw data will be results of CGIC, SSS and SIB-8, along with fMRI results. The study coordinator will develop and maintain common study documents including the protocol, manuals, template consent documents, and policy and procedures memoranda. These documents will ensure that study participants are enrolled, treated, and followed according to the same procedures. The study coordinator will also maintain an official study chronology of important events occurring during the trial, including protocol revisions and serve as the repository for study documents. The PI will monitor submission of the common study protocol to clinic IRB and compliance with study procedures. Study personnel will be trained and certified in study procedures for treatment and data collection before the study begins and training will be reinforced as indicated.

Standards to be used for raw and meta-data format and content

Prior to initiation of participant recruitment, the Data Management Team will develop detailed methods for data collection. Data will be recorded on CRFs. The study coordinator and psychometrician will have primary responsibility for developing, testing, and maintaining the CRFs in collaboration with the PI. Forms will be identified by a participant study ID number and an alpha code to prevent personal identifiers from being transmitted to the Data Management Team. Data will be entered into a data system and the Data Management Team will oversee data storage. Backup files of the database will be stored at regular intervals in a secure, off-site location, to permit regeneration of the database in the event that it is destroyed. CRFs will be available through the study website in real-time. A study investigator will maintain a clinical chart for each participant that will contain source documents including clinical information and progress notes.

Plans for archiving the raw and meta-data, and for ensuring continuous access

The research data will be stored and managed in REDCap, a secure web-based database system designed for clinical research studies. The REDCap database will be developed by the study team, with oversight from the biostatistician ([name]). REDCap will facilitate data archival, data analyses, and data sharing.

STUDY RECORDS RETENTION

Study documents should be retained for 25 years.

